**Timeline:**

- **Timepoint 1 Visit** – will include baseline behavioral assessments, gait tests,

written questionnaires, and fMRI scan

- Training session #1 : [this could occur on the same day as the first behavioral and fMRI sessions]
- Visit 2 – training session #2
- Visit 3 – training session #3
- Visit 4 – training session #4
- Visit 5 – training session #5
- Visit 6 – training session #6
- Visit 7 – training session #7
- Visit 8 – training session #8
- Visit 9 – training session #9
- Visit 10 – training session #10
- Visit 11 – training session #11
- Visit 12 – training session #12
- **Timepoint 2 Visit** – will include endpoint behavioral assessments, gait tests, written questionnaires, and fMRI scan 2 at the end of the intervention . This visit could occur on the same day as the final intervention, or the next day or two per subject and experimenter convenience.–

Each behavioral session will take roughly 1 hour. Each intervention session will take about 1 hour. Each fMRI scan session will take 2 hours. The behavioral and fMRI sessions will take place at WIMR; the training sessions will take place at the UW-Madison Mechanical Engineering Building. We will arrange and pay for transportation between sites as needed.

Evidence suggests that targeted lower limb cycle training can improve walking distance and speed in stroke patients. Some example studies used a program of 10-15 training sessions over 2-3 weeks (Brown et al., 2005; Katz-Leurer et al., 2006), and 12 sessions over 4 weeks have been used in robotic gait training (Krishnan et al., 2013). This basis suggests that the intended duration and intensity of training (12 sessions of 30 minutes over 4 weeks) will be sufficient to demonstrate improvements in gait and motor function if they occur. However, this protocol is a target, which may be adjusted for individual patients as necessary to accommodate schedules and other needs. In such cases, the goal will be to keep the total number of training sessions constant for all patients. However, if interim results [after 6-10 patients] suggest that 12 sessions is not sufficient, then the study team will make provisions to increase the number of study sessions. Finally, if it appears that the subject will take more than 15 sessions to complete the study, then subject participation in the study will end.

### **Aerobic Training Group (Control Group): Procedure**

Patients in the Control group will perform an identical protocol to that used by the Robotic group, except that the robotically-incentivized pedaling exercise will be replaced with an aerobic therapy program. This intervention will emulate an established form of motorized pedaling therapy similar to that used in commercial motorized exercise bikes to improve underlying cardiovascular unfitness contributions to gait impairment. This therapy implements a simple version of assist-as-needed and constant-velocity control. The patient's target pedaling speed (e.g. 20 rev/min (to be finalized through pilot tests: range 15-50 rev/min) and power level (set by heart rate to require approximately 50-70% of maximal oxygen uptake, estimated individually for each patient) are set at the beginning of each session and a motor provides assistance or resistance to compensate for the performance of the patient. The exercise will be performed in this mode for 30 minutes per training session.

### **Healthy Normal Controls**

#### **Non-Stroke Group 1 (Typical Comparison Group): Procedure**

Healthy Normal subjects in this group will be administered the same behavioral measures as the Stroke groups, and 1 fMRI scan while stepping (or imagining stepping) at the beginning of the study. Subjects will then undergo up to 5 training sessions on the robotic cycle with a modified training task. This task will incentivize performance of a novel motor task, such as eccentric force control, mediolateral force control, or EMG coordination in a pattern different from normal cycling. Performance in matching the target task will be evaluated across the training sessions.

#### **Non-Stroke Group 2 (Pilot Group): Procedure**

Healthy Pilot subjects will test the therapeutic tasks as they are designed, as well as a subset of the assessments (e.g. IMU gait data collections). The subjects will provide user feedback on the design of each task, and their data will provide insight into the pattern and time-course of motor learning in healthy subjects.

### **Images and Audio/Video Recording**

Study procedures (behavioral visits and intervention) will be photographed and visibly and audibly recorded. Permission will be obtained from the subject before photographs/recording are commenced. The pictures/recording may be used in the following ways:

- in lab meetings to discuss the subject's progress and possible ways to improve testing
- to assess inter-tester reliability and for training new personnel before they

- administer the behavioral tests
- in research group presentations with collaborators or at conferences to show examples of subjects performing the tasks in this research study
- in publications to illustrate the protocols used in the study.

When possible, photographs and video recordings will be done such that the subject will not be easily identifiable. Identifiable features in images will be electronically obscured before publication.

### **Subject randomization:**

Subjects with stroke will be randomly assigned to the intervention [robotic] or non-intervention [aerobic/control group]. Randomization will be done using a block design. We will control for sex (male vs female) and stroke severity (based on Fugl Meyer assessment) to ensure comparability across groups.

### **Data and Safety Monitoring Plan**

Adverse events or problems will be reviewed by the principal investigator as they occur and reported to the IRB in accordance with posted guidelines at <http://www.grad.wisc.edu/research/hrpp/hsirbs/hs.AdverseEventAndIncidentReporting.html>

The PI and the co-investigators will meet regularly to review the data and safety monitoring plan to ensure adherence to IRB guidelines.

All researchers and research staff involved in the study have completed Human Subjects and HIPAA training and will be continuously involved in data and safety monitoring. Data and safety monitoring will occur on a continuous basis. fMRI and EMG data will be reviewed by the PI, Co-I and a group of study team members on a continuous basis. All behavioral measures will be reviewed by the study team within two weeks of collection.

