***Study Procedure***

***Subject Assessments***

### ***Behavioral Assessment:***

The following commonly used measures of lower extremity motor assessment, standard stroke scales, and measures of activities of daily living will be administered at starting and ending time points to all patients over the length of the study. Healthy normal controls will complete these measures at the beginning of the study. Pilot controls (enrolled before other groups as well as throughout the study for continuing development) will complete a subset as deemed necessary for preparing the study and the study team for the patient and control groups. The assessments are as follows:

1. Six Minute Walk Test (6MWT): The 6MWT is a simple series of laps along a 30 m straight path in a level hallway. Subjects will be instructed to walk as far as they can in six minutes back and forth along this path, according to standard instructions (Rehab Measures - 6 Minute Walk Test). They will be allowed to use mobility aids, to stop or to rest as necessary. Total distance walked will be recorded based on the number of laps (including any fractional last lap), as well as from the IMU motion reconstruction.
2. Timed Up-and-Go test (TUG): The TUG is a simple timed test of how long it takes to stand up, walk 10 feet, turn around, return to the starting point, and sit down. Subjects will be instructed to perform this sequence as quickly as they safely can, using standard instructions (Podsiadlo and Richardson, 1991). The test will be performed in a laboratory or hallway setting.
3. Self-Selected Walking Speed (SSWS): A simple test of the speed a person chooses to walk over a 5-meter distance.
4. Fastest Comfortable Walking Speed (FCWS): A similar test of the “fastest comfortable speed” a person can use to walk over the 5-meter distance

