9. Electromyography (EMG) – is the recording of changes in skin voltage caused by contraction of the underlying muscles. This recording will be obtained using the EMG recording equipment incorporated in the rehabilitation cycle. EMG electrodes will be attached to the surface of the skin over selected muscles of interest in the legs. Muscles may include tibialis anterior, gastrocnemius (medial and lateral), soleus, peroneus longus, peroneus brevis, vastus medialis, vastus lateralis, rectus femoris, iliopsoas, biceps femoris (medial and lateral), semitendinosus, gluteus maximus, gluteus medius, and tensor faciae latae. Proper electrode placement is made according to recommendations from the literature (De Luca, 1997; Rainoldi et al., 2004; SENIAM). A reference electrode will be attached over a bony landmark such as the kneecap, elbow or anterior superior iliac spine (ASIS). Wires will be restrained by tight-fitting clothing, straps or skin-safe tape to prevent motion artifacts. EMG signals will be pre-amplified at the sensor site, and simultaneously recorded by (i) a computer data acquisition system, and (ii) a microcontroller used to control the robotic cycle. Electrodes will be either single-use adhesive electrodes or reusable electrodes. EMG signals will be used as input to the robotic controller as well as for evaluation of outcomes.
10. Leg strength: will be assessed using isometric contractions against the instrumented pedals of the rehabilitation cycle.
11. Health Questionnaire: to document the general physical health and social habits of all subjects.
12. Pain Scale: Patients will be asked to rate their degree of pain on a scale of 0 (no pain) to 5 (in tears).
13. Modified Ashworth Scale: will be used to assess muscle tone in each hip and knee.
14. Fugl Meyer Assessment (FMA): range of motion testing of lower and upper limb capacity. The lower-limb section of the 37-item FMA (11 items) (Hsieh et al., 2007) will be used to categorize stroke severity at the time of block randomization into one group or another. If time allows, the complete 37-item FMA will be performed instead for completeness.

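### No masking of outcome assessors or data processors is described, although the primary walking tests depend on effort and instruction and are held at a different site from training

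*Combined protocol and SAP*

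**What the plan says.** Study Outcomes names the 6MWT, self-selected walking speed (SSWS) and fastest comfortable walking speed (FCWS) as the measures of the primary outcome, with foot-placement variability, symmetry and stability taken from inertial sensors. For the 6MWT, Behavioral Assessment states: "Subjects will be instructed to walk as far as they can in six minutes". Standard instructions are cited there for the 6MWT and the Timed Up-and-Go, but not for SSWS or FCWS.

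Subject randomization says "Randomization will be done using a block design" and adds control for sex and Fugl Meyer severity. It says nothing on masking, and neither does any other section of the text available, which lacks its opening pages.

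The Data and Safety Monitoring Plan says "All behavioral measures will be reviewed by the study team within two weeks of collection" and "fMRI and EMG data will be reviewed by the PI, Co-I and a group of study team members on a continuous basis". Neither sentence carries a masking condition.

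On location, the Timeline says: "The behavioral and fMRI sessions will take place at WIMR; the training sessions will take place at the UW-Madison Mechanical Engineering Building". On the final assessment it says: "This visit could occur on the same day as the final intervention, or the next day or two per subject and experimenter convenience".

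**The concern.** How far a patient walks in six minutes, and what the patient takes to be the fastest comfortable speed, can shift with the tester's wording, tone and encouragement. A tester who knows the arm and hopes the new therapy works can shift them without intending to. Later steps also leave room for choice. No processing rules are given for the gait-stability and symmetry measures, and the laterality index (LI) counts activated voxels without a stated numerical threshold.

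The specific aims compare robotic training with aerobic pedaling, so a bias that differs by arm falls directly on the contrast of interest. The chosen sample size rests on a one-tailed test, so a bias toward the new therapy lies in the direction of rejection.

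**Working it through.** **1. What each section does and does not provide.**

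- *Subject randomization*: blocking, sex and severity. These balance the arms at entry and do not affect how outcomes are measured afterwards.
- *Behavioral Assessment, Gait Assessment, Data Processing/Data Analysis*: none says who tests or who processes.
- *Data and Safety Monitoring Plan*: shows open review by the team. It does not show who assessed the patient.
- *Timeline*: separates the walking tests and scans from training by building, which shows where sessions happen but not who runs them.
- *Images and Audio/Video Recording*: recordings may be used "to assess inter-tester reliability". This suggests more than one tester over the study, but not a tester free of training duties.
- *Leg strength*: "will be assessed using isometric contractions against the instrumented pedals of the rehabilitation cycle". EMG also uses the cycle's equipment. Site separation does not reach these two measures, and they are outside this point.

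**2. The plan's own sample size.** Sample Size uses N per group = 2 × ((z for alpha + z for power) × SD / d)².

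- 6MWT (d = 154.3 m, SD = 171.1 m): two-tailed 2 × (2.80 × 171.1/154.3)² = 19.28, stated 20; one-tailed 2 × (2.49 × 171.1/154.3)² = 15.25, stated 16.
- SSWS (0.21, SD 0.13 m/s): 6.01 and 4.75, stated 6 and 5.
- FCWS (0.18, SD 0.15 m/s): 10.89 and 8.61, stated 11 and 9.
- Dropout: 16/(1 − 0.20) = 20 per group.

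The figures reproduce, apart from rounding 6.01 down to 6. Nothing proposed here changes N.

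**3. Illustration of what a bias would do.** The documents give no bias figure, so every value of b below is an assumption. Suppose the arms truly do not differ and unmasked testing adds a between-arm difference b. With 16 completers per group and the plan's SD, SE = SD × √(2/16). The false-positive rate is 1 − Φ(1.645 − b/SE) one-sided, and 1 − Φ(1.96 − b/SE) + Φ(−1.96 − b/SE) two-sided.

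| Outcome | SE | Assumed b | b/SD | One-sided | Two-sided |
|---|---|---|---|---|---|
| 6MWT | 60.5 m | 5 m | 0.03 | 5.9% | 5.1% |
| 6MWT | 60.5 m | 15 m | 0.09 | 8.1% | 5.7% |
| 6MWT | 60.5 m | 20 m | 0.12 | 9.4% | 6.3% |
| 6MWT | 60.5 m | 30 m | 0.18 | 12.5% | 7.9% |
| 6MWT | 60.5 m | 50 m | 0.29 | 20.7% | 13.1% |
| SSWS | 0.046 m/s | 0.02 m/s | 0.15 | 11.3% | 7.2% |
| SSWS | 0.046 m/s | 0.05 m/s | 0.38 | 28.9% | 19.3% |
| FCWS | 0.053 m/s | 0.02 m/s | 0.13 | 10.2% | 6.6% |
| FCWS | 0.053 m/s | 0.05 m/s | 0.33 | 24.1% | 15.6% |

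The 6MWT tolerates a small bias because its assumed SD is large. The two speed tests have smaller SDs, and no standard instructions are cited for them. The plan ties these SDs to post- versus pre-training differences but uses them in a two-group formula; the table follows that use.

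**The case against.** The strongest reply is that this is a pilot with several safeguards already. The 6MWT follows standard instructions, and its distance is taken from laps and from the sensors. All data carry a subject number. Regions of interest are predefined, the fMRI measures are quantitative so as to avoid a visual read, and a family-wise error method combines threshold with cluster size. All of this stands and narrows the room for bias. It does not keep anyone unaware of arm. A second distance record guards against misrecording, not against uneven encouragement. A subject number hides the name, but nothing says it hides the arm. A quantitative measure still needs its threshold set.

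A reader might go further than the documents allow:

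- *The same people build the device, train patients and test them.* No roles are given, so this is not shown.
- *Masking needs no extra staff.* No staff numbers are given. Separate buildings and a reference to several testers make it plausible but do not establish it.
- *Testers decide when a rest ends, or analysts exclude strides.* The 6MWT lets patients rest as they need within a fixed six minutes, and no stride-exclusion step appears.
- *Thresholds are set patient by patient with arm known.* The text leaves the number open but does not say this.

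It is also fair to object that masking everyone until the data are locked would conflict with the interim look after 6 to 10 patients, the changes to the task based on early patients, and continuous review of fMRI and EMG. The fix must allow for these.

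**Conclusion.** The point holds as an omission that leaves effort-dependent primary outcomes, and the processing of sensor and scan data, open to arm-related bias. It should be corrected, because the trial's aims are between-arm comparisons and the remedy leaves sample size, visits and treatment unchanged. Pilot status lowers the stakes but does not remove the problem.

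The size is unknown. The error rates in the table are conditional on assumed biases, no true difference, 16 completers per group and the plan's SDs. They show sensitivity and are not evidence that bias will occur. The conclusion does not rest on the same staff both training and testing.

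**What to change.** 1. Process the sensor gait data and the fMRI region-of-interest data (percent signal change and LI) under codes that hide arm and, where possible, time point. Fix the processing and threshold rules before arm is revealed.
2. Extend the scripted standard instructions to SSWS and FCWS.
3. Where the current team's rota allows, have the Timepoint 2 walking tests run by an existing member who did not train that patient and is not told the arm. Ask patients not to mention their training.
4. State that staff who deliver training, review safety or carry out the interim look may know the arm but do not process the coded outcome data.
5. State in Subject randomization who is masked and who is not. If the tester cannot be masked, give the reason, keep the masked processing and report that testing was unmasked.

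The cost is a coding step and rota planning. If the same few people do everything, roles would have to be divided, and the documents do not show how hard that would be. Some patients will reveal their arm; the coded processing still protects the later steps when they do.

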### **Data Processing/Data Analysis**

#### ***Behavioral Data:***

For the analysis of pre- and post- measures on the behavioral data, we will perform repeated measures ANOVA tests with time as the independent variable and score on

each behavioral test as the dependent variable.

In order to assess the overall effect of the rehabilitation protocol, we will perform multiple regression analyses to determine the extent to which data from each modality explains the proportion of the variance in the behavioral outcomes. The dependent variable is the score on the behavioral test and the predictors are the task tracking performance (error) in EMG and foot force during the last training session, and the percent signal change in targeted brain areas from the fMRI data.

In addition, we will also perform a multivariate ANOVA to examine the mixed model with Time of testing (pre, post) as a within subject factor, Group (robotic therapy, aerobic therapy) as the between-subject factor, and dependent variables of percent signal change from the fMRI data and each of the behavioral scores. This will help us to determine if there is a significant difference between the groups in terms of behavioral performance and functional activations and also to determine whether these dependent measures change over time.

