***fMRI data:***

SPM5 (Wellcome Department of Cognitive Neurology, London, UK) will be employed for motion correction and used to normalize the EPI BOLD images to a standard space using a 12 parameter linear transformation. The images will be then spatially smoothed using an 8.0 mm Gaussian kernel. Finally, the statistical package contained within SPM5 will be used to estimate the effects of condition at each voxel according to the general linear model. The analysis will be entered into SPM5 as an epoch design of the fixed response/box car form convolved with canonical HRF, reflecting the appropriate activation and rest periods within the total scanning period. Images will be high-pass filtered at 128 s to remove low- frequency drifts in blood oxygen level-dependent signal.

Percent signal change (after vs. before) will be compared statistically between the two groups using unpaired two-sample t-tests between the robotic and aerobic groups. A repeated measures ANOVA will be performed with the dependent variable being the percent signal change and between subjects factor Group (robotic therapy, aerobic therapy), and within subject factor Time (before and after training).

Along with percent signal change over time, we will also compute region-wise laterality index. ROIs will be predefined in each hemisphere. For each ROI, laterality index (LI) will be defined as: Number of activated voxels in the affected hemisphere / [voxels in the left hemisphere + voxels in the right], thus giving LI for each ROI. LI = 0.5 indicates symmetrical activation; LI < 0.5 indicates an activation deficit on the affected side, and LI > 0.5 indicates increased activation of the affected side. This index will provide a way of

understanding the contribution of each brain area (ROI) to the overall task-related activation in one session and changes in laterality over time. The percent signal change and LI are purely quantitative measures, in order to ensure that change in plasticity over time is captured adequately and does not rely on individual fMRI reader's abilities to gauge these changes simply on the basis of a "visual read" of the fMRI scans.

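### The behavioural analysis section isolates no between-arm contrast, estimate or confidence interval for gait, although comparing the arms on gait is the primary objective

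*Combined protocol and SAP*

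**What the plan says.** Under Study Objectives, the primary objective is the effect of robotic pedaling on lower-limb function during pedaling and walking, compared with aerobic pedaling. Under Study Outcomes, the primary outcome is gait function from the six-minute walk test (6MWT), self-selected walking speed (SSWS) and fastest comfortable walking speed (FCWS), with sensor-based gait measures also of interest.

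The Behavioral Data section gives three analyses:

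1. For pre and post scores, "we will perform repeated measures ANOVA tests with time as the independent variable" and each test score as the dependent variable.
2. "In order to assess the overall effect of the rehabilitation protocol, we will perform multiple regression analyses". Here the score is the dependent variable and "the predictors are the task tracking performance (error) in EMG and foot force during the last training session", together with fMRI signal change in the targeted brain areas.
3. As an addition, a multivariate ANOVA with Time within subjects, Group between subjects, and "dependent variables of percent signal change from the fMRI data and each of the behavioral scores". Its stated purpose includes finding out "if there is a significant difference between the groups in terms of behavioral performance and functional activations".

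The fMRI data section treats the secondary outcome differently. Percent signal change "will be compared statistically between the two groups using unpaired two-sample t-tests between the robotic and aerobic groups", followed by a repeated measures ANOVA on that variable alone with "between subjects factor Group (robotic therapy, aerobic therapy), and within subject factor Time (before and after training".

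The Subject randomization section adds: "We will control for sex (male vs female) and stroke severity (based on Fugl Meyer assessment) to ensure comparability across groups". Neither factor appears in any analysis model.

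**The concern.** A comparative objective needs a comparative analysis of its own outcome. The two analyses run on each score contain no group term, so they can describe change or its correlates but cannot say whether robotic training did better than aerobic training. The one behavioural model with Group combines gait with cognition, mood, balance, other scores and fMRI.

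Two things are at stake. If that model is significant, the result does not show whether gait was the source or how large the gait difference was. If it is not significant, a real gait difference may have been diluted by variables on which the arms do not differ. In both cases the trial could report without the one number its primary objective asks for, which is the between-arm difference in gait with its uncertainty. The Subject identification and Recruitment section refers to a later full-scale study, and that study would need the same number.

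**Working it through.** **The plan's own figures.** The Sample Size section uses N per group = 2 × ((z₁₋α/₂ + z_power) × σ/d)², with 1.96 and 0.84 (two-tailed) or 1.65 and 0.84 (one-tailed).

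| Outcome | d ± σ | Two-tailed N (stated) | One-tailed N (stated) |
|---|---|---|---|
| 6MWT | 154.3 ± 171.1 m | 19.28 (20) | 15.25 (16) |
| SSWS | 0.21 ± 0.13 m/s | 6.01 (6) | 4.75 (5) |
| FCWS | 0.18 ± 0.15 m/s | 10.89 (11) | 8.61 (9) |

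These reproduce, apart from the rounding of 6.01 to 6. Enrolment is 16/(1 − 0.20) = 20 per group. The section defines d as post- versus pre-training change, so it neither states a between-arm difference nor names a between-arm gait test.

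**Analyses side by side.**

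| Analysis | Outcome | Group term? |
|---|---|---|
| Repeated measures ANOVA | each behavioural score | no |
| Multiple regression | each behavioural score | no |
| MANOVA | fMRI and all behavioural scores jointly | yes |
| Unpaired t-test | fMRI signal change alone | yes |
| Repeated measures ANOVA | fMRI signal change alone | yes |

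No row tests gait alone with a group term.

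**How well the joint model tests gait.** Assumptions: only 6MWT change differs between arms, by the plan's pre-post figure; ± 171.1 m is the SD of change; the other dependent variables are uncorrelated with it; 16 per arm; two-sided 5%.

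- Standardised difference: 154.3/171.1 = 0.902.
- Noncentrality: (16/2) × 0.902² = 6.51.
- With p dependent variables, the Hotelling test refers to F with p and 32 − p − 1 degrees of freedom.

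| Dependent variables | Degrees of freedom | Power |
|---|---|---|
| 1 (6MWT only) | 1, 30 | 69% |
| 4 | 4, 27 | 43% |
| 10 | 10, 21 | 24% |
| 15 | 15, 16 | 17% |

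The plan does not count its dependent variables. It lists 15 assessments, some of which yield several scores and some none, so the table shows a range.

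**Whether the time-only test can stand in.** Suppose the arms are identical and each gains half the plan's change, 154.3/2 = 77.15 m. Assume the arms are pooled with 32 completers; the plan does not say whether they are. The noncentrality is (77.15/171.1) × √32 = 0.451 × 5.657 = 2.55 on 31 degrees of freedom, giving a significant result about 70% of the time. This is power for a real change over time, not a false-positive rate. It shows that a significant result carries no information about a difference between arms.

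**Power of a gait-only test over a range.** Normal approximation, two-sided 5%, 16 per arm, 6MWT: z = f × 0.902 × √8, where f is the between-arm difference as a fraction of the plan's pre-post change.

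| f | z | Power |
|---|---|---|
| 1.00 | 2.55 | 72% |
| 0.75 | 1.91 | 48% |
| 0.50 | 1.28 | 25% |

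The exact t calculation at f = 1 gives the 69% shown above.

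**Precision of the baseline-adjusted model.** This was simulated for 6MWT with 16 per arm, SD of change 171.1 m, equal pre and post variances, and sex and severity in the model but not prognostic. The pre-post correlation is not in the documents, so three values are shown. Entries are the mean half-width of the 95% confidence interval.

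| Assumed correlation | Adjusted model, covariates balanced | Change score |
|---|---|---|
| 0.5 | about 108 m | about 122 m |
| 0.7 | about 115 m | about 122 m |
| 0.9 | about 122 m | about 122 m |

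If sex and severity are unbalanced between arms, the adjusted half-width at 0.9 is about 126 m.

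**The case against.** The strongest reply is that the plan does compare the arms on behaviour. Its MANOVA has Group and Time, lists each behavioural score, and states that it is meant to find group differences in behavioural performance and changes in the dependent measures. Those factors match the fMRI ANOVA, and the authors may well intend to examine each score within that model. A reader might infer from the time-only ANOVA that the plan contains no arm comparison of behaviour at all, or can yield no gait result that compares the arms. The documents do not support that: it holds only if the MANOVA is read strictly as an omnibus test. What remains is that no follow-up, contrast or estimate for gait is written down.

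A reader might also infer that the arms will be compared by setting one within-arm p-value beside the other. The plan nowhere proposes this.

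Third, this is a pilot, intended partly to choose among therapy designs, and some looseness is reasonable. But it is randomised, sets 80% power at the 0.05 level and looks for significant group differences. A pilot also needs the between-arm estimate and its interval.

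Finally, baseline adjustment might be called a preference, since a Group by Time test would also serve. That is partly right: the gain in precision is modest and disappears at high pre-post correlation.

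**Conclusion.** The point holds as a gap in specification. The primary comparison has no isolated gait contrast, estimate or confidence interval, while the secondary fMRI outcome has its own between-arm test. This conclusion follows from the text and depends on none of the assumed figures.

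The gap has a practical cost if the MANOVA is used as an omnibus test: power for a difference confined to 6MWT falls from 69% to between 43% and 17% with 4 to 15 dependent variables. Those figures treat the plan's pre-post change as the arm difference and assume the other variables are uncorrelated with 6MWT; a different correlation structure would change them. Because the documents give no between-arm difference, no single power figure should be taken as the trial's power.

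The point concerns gait. It does not cover the pedaling part of the primary objective.

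**What to change.** For each of 6MWT, SSWS and FCWS, specify as the primary gait analysis a model of the Timepoint 2 value on group and the Timepoint 1 value, adjusted for the randomisation factors sex and Fugl-Meyer severity. Report the robotic-minus-aerobic difference with a two-sided 95% confidence interval. At minimum, add a gait-only Group by Time test like the one already written for fMRI; that alone closes the gap. Label the time-only ANOVA as descriptive of change and the MANOVA as supportive. Show power over a range of between-arm differences.

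The cost is a little more analysis work and no new data. The adjusted model should not be presented as a large gain: it offers none when the pre-post correlation is near 0.9, and a slight loss there if the covariates are unbalanced.

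Optional, and outside this point: name one deciding gait outcome or apply Holm across the three, and state the role of the sensor-based measures.
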